### 5.2.1 Time to events definition

All the time-to-event variables listed and defined below will be calculated for each subject. Subject who do not achieve the corresponding event will be censored. Details of the censored data are listed in the table 5 below.

**Table 5: Time to event definitions and censored data**

Variables	Definition	Censored data
HBsAg Response	Time to a HBsAg level of $<1000$ IU/mL	Subjects who did not achieve “HBsAg $<xxx$ IU/mL” will be censored at the last HBsAg assessment
	Time to a HBsAg level $<100$ IU/mL	
	Time to a HBsAg level $<10$ IU/mL	
	Time to a HBsAg level $<0.05$ IU/mL	
HBsAg Reduction	Time to a HBsAg reduction of $> 0.3 \log_{10}$ IU/mL	Subjects who did not reduce HBsAg by “ $>xxx \log_{10}$ IU/mL” from baseline will be censored at the last HBsAg assessment
	Time to a HBsAg reduction of $> 0.5 \log_{10}$ IU/mL	
	Time to a HBsAg reduction of $> 1 \log_{10}$ IU/mL	
	Time to a HBsAg reduction of $> 2 \log_{10}$ IU/mL	
	Time to a HBsAg reduction of $> 3 \log_{10}$ IU/mL	
HBsAg Seroclearance (in all subjects)	Time to HBsAg seroclearance as defined in section 5.3.1	Subjects who did not achieve HBsAg seroclearance will be censored at the last HBsAg assessment
HBeAg Seroclearance (in HBeAg-positive subjects only)	Time to HBeAg seroclearance as defined in section 5.3.1	Subjects who did not achieve HBeAg seroclearance will be censored at the last HBeAg assessment
HBeAg Reduction	Time to a HBeAg reduction of $> 0.5 \log_{10}$ IU/mL from baseline	Subjects who did not achieve “HBeAg $<xxx$ IU/mL” from baseline will be censored at the last HBeAg assessment
	Time to a HBeAg reduction of $> 1 \log_{10}$ IU/mL from baseline	
	Time to a HBeAg reduction of $> 2 \log_{10}$ IU/mL from baseline	
HBV virological breakthrough	Time to HBV virological breakthrough as defined in section 5.3.1	Subjects who did not achieve HBV virological breakthrough will be censored at the last HBV DNA assessment during the defined time frame

HBV DNA Response	Time to a HBV DNA level <1 log10 IU/mL	Subjects who did not achieve “HBV DNA <xx log 10” will be censored at the last HBV DNA assessment
	Time to a HBV DNA level <2 log10 IU/mL	
	Time to a HBV DNA level <3 log10 IU/mL	
	Time to a HBV DNA level <100 IU/mL	Subjects who did not achieve “HBV DNA<xxxx IU/mL” will be censored at the last HBV DNA assessment
	Time to a HBV DNA level <1000 IU/mL	
	Time to a HBV DNA level <2000 IU/mL	
	Time to a HBV DNA level <20000 IU/mL	
	Time to HBV DNA < LLQ for target detected and not detected	Subjects who did not achieve HBV DNA<LLQ for both target will be censored at the last HBV DNA assessment
	Time to HBV DNA < LLQ for target not detected	Subjects who did not achieve HBV DNA<LLQ for target not detected will be censored at the last HBV DNA assessment
	Time to HBV DNA < LLQ for target detected	Subjects who did not achieve HBV DNA<LLQ for target detected will be censored at the last HBV DNA assessment
HBV DNA Reduction	Time to a HBV DNA reduction of > 1 log10 IU/mL from baseline	Subjects who did not reduce “HBV DNA by >x log 10 IU/mL” from baseline will be censored at the last HBV DNA assessment
	Time to a HBV DNA reduction of > 2 log10 IU/mL from baseline	
	Time to a HBV DNA reduction of > 3 log10 IU/mL from baseline	
HBV RNA Response	Time to a HBV RNA level <100 cp/mL	Subjects who did not achieve “HBV RNA<xxxx cp/mL” will be censored at the last HBV RNA assessment
	Time to a HBV RNA level <1000 cp/mL	
	Time to a HBV RNA level <2000 cp/mL	
	Time to a HBV RNA level <20000 cp/mL	
	Time to HBV RNA target not detected	Subjects who did not achieve HBV RNA target not detected will be censored at the last HBV RNA assessment
	Time to HBV RNA < LLOQ	Subjects who did not achieve HBV RNA <LLOQ will be censored at the last HBV RNA assessment
	Time to a HBV RNA level <250 cp/mL	Subjects who did not achieve HBV RNA <250IU/ml will be censored at the last HBV RNA assessment
HBV RNA Reduction	Time to a HBV RNA reduction of > 1 log10 cp/mL from baseline	Subjects who did not reduce HBV RNA by “>xx log 10 cp/mL” from baseline will be censored at the last HBV RNA assessment
	Time to a HBV RNA reduction of > 2 log10 cp/mL from baseline	
	Time to a HBV RNA reduction of > 3 log10 cp/mL from baseline	

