Treatment with JNJ-56136379 may lead to emergence of viral variants with reduced susceptibility or resistance to JNJ-56136379. Based on pre-clinical data, these variants remain susceptible to TDF and ETV but might affect treatment options with CAMs in the future.

As of 6 February 2019, virological breakthrough, as defined by the protocol (ie, confirmed on-treatment HBV DNA increase  $>1 \log_{10}$  from nadir level or confirmed on-treatment HBV DNA level  $>200$  IU/mL in subjects who had HBV DNA level below the LLOQ of the HBV DNA assay), was observed in 5 out of the 28 subjects on JNJ-56136379 75 mg monotherapy. In addition, there were 2 subjects who met the virological breakthrough threshold but, due to the change of treatment, the virological breakthrough could not be confirmed. The virological breakthrough in these subjects is expected to be associated with viral resistance to JNJ-56136379. An HBV DNA decline was observed in these subjects upon initiation of NA treatment confirming pre-clinical data showing that viral variants resistant to JNJ-56136379 remain susceptible to NA treatment.

Given the virological breakthroughs observed in the JNJ-56136379 75 mg monotherapy arm (Treatment Arm 1), this treatment arm was discontinued early per Protocol Amendment 4. All subjects were to stop further dosing with JNJ-56136379 75 mg, start treatment with NA, and enter the post-treatment follow-up phase (Schedule 1).

In addition, per Protocol Amendment 4, the duration of treatment with JNJ-56136379 250 mg monotherapy has been limited to a maximum of 24 weeks (see Section 6.1). As an additional precautionary measure to safeguard the subjects, a stringent futility rule has been implemented in the JNJ-56136379 250 mg monotherapy arm (see Section 6.2).

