**Part A:**

Approximately 70 subjects who are currently not being treated for their CHB infection will be randomized in a 3:1:3 ratio to receive one of the following treatments:

- Treatment Arm 1: JNJ-56136379 (N=30) (open-label)

After full recruitment, this treatment arm was discontinued early per Protocol Amendment 4. All subjects were to stop further dosing with JNJ-56136379 75 mg, start treatment with NA, and enter the post-treatment follow-up phase (Schedule 1).

- Treatment Arm 2: Placebo + NA (ETV or TDF) (N=10)
- Treatment Arm 3: JNJ-56136379 + NA (ETV or TDF) (N=30)

At the same time, approximately 40 subjects who are virologically suppressed by current NA treatment will be randomized in a 1:3 ratio to receive one of the following treatments:

- Treatment Arm 4: Placebo + NA (ETV or TDF) (N=10)
- Treatment Arm 5: JNJ-56136379 + NA (ETV or TDF) (N=30)

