### **2.1. Analysis Sets**

*Screened Population or all subjects* consists of all subjects, i.e. screening failures and (not) randomized subjects.

---

*Safety population* consists of all subjects who received at least one dose of the study agent and all safety endpoints will be analyzed by the treatment arm as treated.

*Intent-to-Treat Population (ITT)*: all subjects who are randomized and received at least one dose of any study agent. If a subject receives a study agent other than their randomly assigned study agent, subjects will be shown in the treatment arm as randomized.

The analysis population will be indicated in the title of each table and listing.

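### SAP Table 5 sets no time limit on its response and reduction rows, so a first response reached after NA starts is credited to JNJ-56136379 monotherapy (Arms 1 and 6)

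*SAP*

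**What the plan says.** The SAP's time-to-event section (under 5.3) opens with: "All the time-to-event variables listed and defined below will be calculated for each subject". It names no phase or period. In Table 5 the response and reduction rows for HBsAg, HBeAg, HBV DNA and HBV RNA all censor non-achievers at the last assessment of the marker. The HBV DNA <LLQ row reads: "Subjects who did not achieve HBV DNA<LLQ for both target will be censored at the last HBV DNA assessment".

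Two kinds of row differ. The breakthrough row carries a limit: "Subjects who did not achieve HBV virological breakthrough will be censored at the last HBV DNA assessment during the defined time frame". The two seroclearance rows refer back to the parameter definitions in 5.3, which tie that outcome to Week 24 or Week 48 of treatment.

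For the ITT population, SAP 2.1 says that "subjects will be shown in the treatment arm as randomized". SAP Table 1 ends the treatment phase 5 days after the last study agent intake (JNJ-56136379 or placebo) and runs follow-up to last contact or an interim cut-off.

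Monotherapy subjects receive NA during that time:
- **Arm 1** (Protocol 3.1): "All subjects were to stop further dosing with JNJ-56136379 75 mg, start treatment with NA, and enter the post-treatment follow-up phase".
- **Arm 6, extended** (Protocol 6.1): NA is added from Week 24 to Week 48 while JNJ-56136379 continues.
- **Arm 6, futility rule** (Protocol 6.2): one breakthrough in the first 24 weeks leads to NA being added for all remaining subjects.
- **Not extended, or stopped early** (Protocol 3.1 and 6.1): NA should be started, following local guidelines.

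Follow-up Schedule 1 measures HBV DNA at follow-up Weeks 2, 4, 12 and 24.

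**The concern.** The SAP's main comparisons (5.2.1.1) concern 24 weeks of monotherapy against placebo+NA and against the combination. Both comparators contain NA from Day 1. If the monotherapy clock keeps running after NA is given, a subject who failed on monotherapy and first reached <LLQ on NA is a monotherapy responder. The monotherapy arm then moves toward the NA-containing arms because its failures were given NA.

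Protocol 1.3.4 shows that the mechanism is real. Of the subjects with breakthrough on 75 mg it says: "An HBV DNA decline was observed in these subjects upon initiation of NA treatment". The SAP tabulates anti-HBV NA rescue as a concomitant medication of interest (4.4), but no efficacy derivation uses it.

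**Working it through.** The plan gives no event count, power or alpha for these variables, so there is no figure to reproduce. The check has four parts.

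**1. Does another passage supply the missing limit?** The opening of SAP 5 says virology and serology data are analyzed by phase, period and follow-up type, where applicable. Table 4 (response proportions) writes out its own within-phase rule. Table 5 has no such rule and instead names an explicit censoring date, the last assessment. A treatment-phase cut would also not be enough: in Arm 6, NA is added while study agent continues, so NA-era responses fall inside the treatment phase.

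**2. Length of the window.** For a Week 24 completer who is not extended: 24 weeks on monotherapy + 24 weeks of follow-up, normally on NA = 48 weeks. A first response can be counted over 48/24 = 2 times the intended period.

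**3. Possible size (assumptions).** Let m be the proportion reaching <LLQ on monotherapy and q the proportion of the rest who first reach it after NA starts. Then credited proportion = m + (1 − m)q, NA-era events = N(1 − m)q, and NA-era share = (1 − m)q / [m + (1 − m)q]. N = 30 is the planned size of Arm 1, and Arm 6 follows the same format. The two lower values of m are the Phase 1 Day 29 rates in Protocol 1.1 (3/12 at 75 mg, 5/12 at 250 mg). They are anchors only, because Day 29 is not Week 24. The other values of m, and q from 0.5 to 0.9, are assumed.

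| m (proportion if cut at NA start) | credited if uncut, q = 0.5 to 0.9 | NA-era events of 30 | share of credited responses |
|---|---|---|---|
| 3/12 = 0.25 | 0.625 to 0.925 | 11.2 to 20.2 | 60% to 73% |
| 5/12 = 0.42 | 0.71 to 0.94 | 8.7 to 15.7 | 41% to 56% |
| 0.60 | 0.80 to 0.96 | 6.0 to 10.8 | 25% to 38% |
| 0.80 | 0.90 to 0.98 | 3.0 to 5.4 | 11% to 18% |

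**4. Would censoring at NA start be enough?** Take the 28 Arm 1 subjects in Protocol 1.3.4 and assume that 18 respond on monotherapy and 10 do not. Suppose 9 respond, then the 10 non-responders start NA and are censored, then the other 9 respond.
- Kaplan-Meier: 19/28 × 0/9 = 0 event-free, so cumulative response is 100%.
- Competing event: 9/28 + (9/28 × 9/9) = 18/28 = 64%.
- Uncut, if all 10 later respond on NA: 28/28 = 100%.

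Kaplan-Meier gives 64% only when all 18 respond before any of the 10 is censored. Protocol 10.2 (criteria 11 and 12) stops JNJ-56136379 for weak HBV DNA decline or breakthrough, so NA start is linked to failure and censoring there is informative.

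**The case against.** The case on the other side has real force.

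- **Other text may cover it.** The general split in SAP 5 by phase and period could be meant to include Table 5. That makes the omission look like a lapse in drafting. It does not override a stated censoring rule, and it does not reach NA added within Arm 6's treatment phase.
- **No output is shown to be affected.** The secondary analysis list in SAP 5.3 names no time-to-event curve, test or table, and Protocol 11.3.3 makes the method optional. The choice of output for each analysis is left to a separate specification document that is not available here. This stands, and it limits the weight of the point. The SAP nevertheless commits to deriving the variables.
- **Following subjects as randomized is legitimate.** The protocol's endpoints cover treatment and follow-up. This stands too, provided that such an analysis is labelled and is not presented as the effect of monotherapy.

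Some stronger inferences are tempting, but the documents do not support them:

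- *Every Table 5 row is affected.* The breakthrough and seroclearance rows have their own time frames. Phase 1 mean HBV DNA decline at Day 29 was 2.89 log10 at 75 mg and 2.70 at 250 mg, so many >1 and >2 log10 reductions would come before NA. Protocol Table 7 assumes mean HBsAg changes on NA of only −0.05 to −0.35 log10 at Week 24, so most HBsAg rows are little exposed. The >0.3 log10 row in HBeAg-positive subjects is a possible exception.
- *All 28 Arm 1 subjects can add NA-era events.* In 5 of the 28, breakthrough had already been confirmed, and the Amendment 4 rationale says they had stopped 75 mg and started NA. Anyone who met a threshold on monotherapy cannot meet it for the first time on NA. Protocol 1.3.4 also reports a decline on NA, not <LLQ.
- *The distortion is 64% against 100%.* That contrast rests wholly on the assumed 18/10 split.

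**Conclusion.** The concern holds in a limited form. As written, the response and reduction rows of Table 5 credit JNJ-56136379 monotherapy with first responses reached after NA is started (Arm 1, and Arm 6 subjects who stop) or added (Arm 6 on continued treatment). The effect is plausible mainly for low HBV DNA thresholds such as <LLQ. It raises apparent response in the monotherapy arms and so narrows the gap to the NA-containing arms.

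The size cannot be taken from the documents. The range of 11% to 73% of credited responses depends on assumed values of m and q. This is a supportive secondary analysis, and Table 5 does not feed the Week 24 HBsAg primary endpoint. The change is worth making before the variables are derived.

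**What to change.** Add to SAP Table 5, for the response and reduction rows:

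1. **Monotherapy arms (1 and 6).** An event counts only if it occurs before the earlier of first on-study NA intake and the end of the SAP treatment phase (last study agent intake + 5 days). NA start, or stopping monotherapy, without a response is a competing event: report cumulative incidence, with the subject remaining a non-responder. Ordinary censoring stays for subjects still on monotherapy at an interim cut-off.
2. **Comparisons with these arms.** Limit all arms to the same treatment-phase window. From about Week 24 the Arm 6 curve can only stay flat, so the contrast is best read at Week 24, the horizon of the main comparisons.
3. **Uncut version.** Keep it as a separate display labelled treatment-policy, including post-NA and follow-up responses in all arms. The combination arms' follow-up data are then not lost.

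Cost: one derivation rule, one extra display, and fewer events in the monotherapy arms. No new data are needed, because NA intake is already captured in the exposure and concomitant medication listings (SAP 4.4 and 4.6).

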**Table 4: response categories for viral activity parameters**

	Category criteria	Additional info
HBsAg Response	Subject who has achieved a HbsAg level <1000 IU/mL per time point	These proportions will also be included per analysis phase and analysis period. A subject will be included in the numerator if the response category is at least once met within the analysis phase/period.
	Subject who has achieved a HbsAg level <100 IU/mL per time point	
	Subject who has achieved a HbsAg level <10 IU/mL per time point	
	Subject who has achieved a HbsAg level <0.05 IU/mL per time point	
HBV DNA Response	Subject who has achieved a HBV DNA level <1 log10 IU/mL per time point	These proportions will also be included per analysis phase and analysis period. A subject will be included in the numerator if the response category is at least once met within the analysis phase/period.
	Subject who has achieved a HBV DNA level <2 log10 IU/mL per time point	
	Subject who has achieved a HBV DNA level <3 log10 IU/mL per time point	
	Subject who has achieved a HBV DNA level <20 IU/mL per time point	
	Subject who has achieved a HBV DNA level <60 IU/mL per time point	
	Subject who has achieved a HBV DNA level <100 IU/mL per time point	
	Subject who has achieved a HBV DNA level <1000 IU/mL per time point	
	Subject who has achieved a HBV DNA level <2000 IU/mL per time point	
	Subject who has achieved a HBV DNA level <20000 IU/mL per time point	
	Subject who has achieved a HBV DNA level < LLQ for target detected and not detected per time point	
	Subject who has achieved a HBV DNA level < LLQ for target not detected per time point	
	Subject who has achieved a HBV DNA level < LLQ for target detected per time point	
HBV RNA Response	Subject who has achieved a HBV RNA level <100 cp/mL per time point	These proportions will also be included per analysis phase and analysis period. A subject will be included in the numerator if the response category is at least once met within the analysis phase/period.
	Subject who has achieved a HBV RNA level <1000 cp/mL per time point	
	Subject who has achieved a HBV RNA level <2000 cp/mL per time point	
	Subject who has achieved a HBV RNA level <20000 cp/mL per time point	
	Subject who has achieved HBV RNA target not detected per time point	
	Subject who has achieved HBV RNA < LLOQ per time point	
	Subject who has achieved a HBV RNA level <250 cp/mL at week 24	

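### HBV DNA below LLQ with target detected is an intermediate state, so as a response and a time-to-event it can rank a more potent arm lower

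*SAP*

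**What the plan says.** SAP Table 4 (response categories, under 5.3) lists three HBV DNA responses below the quantification limit:

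- combined: "Subject who has achieved a HBV DNA level < LLQ for target detected and not detected per time point"
- not detected only: "Subject who has achieved a HBV DNA level < LLQ for target not detected per time point"
- detected only: "Subject who has achieved a HBV DNA level < LLQ for target detected per time point"

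Each is tabulated by visit and also by phase and period, where "A subject will be included in the numerator if the response category is at least once met within the analysis phase/period".

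Table 5 turns the same three into time-to-event variables, including "Time to HBV DNA < LLQ for target detected" and the combined "Time to HBV DNA < LLQ for target detected and not detected". The general rule above the table is "Subject who do not achieve the corresponding event will be censored". The detected-only row repeats it: "Subjects who did not achieve HBV DNA<LLQ for target detected will be censored at the last HBV DNA assessment". Neither table says that a not-detected result counts as having met or passed the detected-only category, and no competing-event rule is given.

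SAP 5.1 sets the quantification limit at 20 IU/mL. It assigns 15 IU/mL to results below it with target detected, and 5 IU/mL to results with target not detected.

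**The concern.** The numeric HBV DNA thresholds in these tables, and the combined below-LLQ row, are one-sided: a lower value always qualifies. The not-detected row is the bottom of the scale. The detected-only row is different, because it has a floor as well as a ceiling and a better result fails it. Three consequences follow from the text:

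- A subject who falls from a quantifiable level to not detected between two visits is a non-responder in Table 4 and censored in Table 5, although suppression is deeper.
- A subject who moves from detected to not detected loses the per-visit response on this row.
- A subject first seen below LLQ as not detected, who later rebounds to detected, is recorded as achieving the event at the rebound.

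The censoring is also tied to outcome, since some subjects are censored because they did better. At stake is a secondary output row, labelled as an achievement and shown by arm and dose, whose direction cannot be interpreted on its own.

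**Working it through.** The plan states no rate, power or alpha for this endpoint, so there is no figure to reproduce. The check has a part from the text and an illustrative part.

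**From the text.** log10(15) = 1.18 and log10(5) = 0.70, against log10(20) = 1.30 for the limit. On the SAP's own scale, not detected lies below detected, so the detected-only state is the middle of three. Protocol Time and Events footnote ee puts visits at Weeks 1, 2, 4, 8, 12, 16, 20 and 24, so after Week 4 a subject has four weeks in which to cross the band unobserved.

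**Constructed example (assumed counts, 30 per arm).**

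| | Straight to not detected | Seen as detected | Never below LLQ | Detected-only row | Combined row |
|---|---|---|---|---|---|
| More potent arm | 18 | 9 | 3 | 9/30 = 30% | 27/30 = 90% |
| Weaker arm | 6 | 15 | 9 | 15/30 = 50% | 21/30 = 70% |

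**When the order reverses.** Let p be the share ever below LLQ and s the share of those never seen as detected. The detected-only share is p(1 − s). With assumed p = 0.90 in the better arm and 0.70 in the weaker arm, the better arm looks worse once its s exceeds 1 − 0.70(1 − s_weak)/0.90:

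- s_weak = 0.10: 1 − 0.63/0.90 = 0.30
- s_weak = 0.20: 1 − 0.56/0.90 = 0.38
- s_weak = 0.30: 1 − 0.49/0.90 = 0.46

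**Simulation at the protocol visits to Week 24.** All inputs are assumptions: log10 HBV DNA = baseline − a(1 − exp(−t/1.5)) − bt + noise (SD 0.1), with t in weeks and (a, b) = (2.2, 0.12) for the slower arm and (2.8, 0.24) for the faster arm. In every row the faster arm has 100% ever below LLQ.

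| Baseline, log10 (uniform) | Detection limit, IU/mL | Ever detected-only, slower | Ever detected-only, faster |
|---|---|---|---|
| 4–7 | 10 | 49% | 29% |
| 4–7 | 5 | 77% | 59% |
| 5–8 | 10 | 30% | 30% |
| 5–8 | 5 | 45% | 60% |
| 6–9 | 10 | 10% | 31% |
| 6–9 | 5 | 13% | 61% |

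In the first row, 79% of the slower arm are ever below LLQ. All of the faster arm are not detected at Week 24, yet 71% of that arm never register on the detected-only row.

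A second model, with a graded detection probability and normally distributed baselines, gave the same mixed picture. As the decline rate rose from 1.0 to 1.6 times, ever detected-only went from 71% to 54% at mean baseline 4.5 log10, while ever below LLQ went from 85% to 99%. At mean baseline 6.5, ever detected-only rose instead: 37%, 61% and 66% at 1.0, 1.3 and 1.6 times.

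**The case against.** The strongest reply is that the right answers are already beside the doubtful one. Tables 4 and 5 carry the combined and not-detected rows, Table 4 also has a row for below 20 IU/mL, and a subject who goes straight to not detected is an achiever on all of them. The SAP's secondary analysis section names no Kaplan-Meier, log-rank or Cox comparison for the Table 5 variables; protocol 11.3.3 says only that time-to-event methods may be used. The list of proportions for differences and confidence intervals includes HBV DNA reduction but not these response categories. The study is exploratory, the primary endpoint is HBsAg change at Week 24, and continuous HBV DNA is imputed in the correct order. All of this stands, and it limits the consequence to a misleading row.

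It does not remove the defect. The SAP commits to calculating every listed time and tabulating every response category by visit and by period, so the row will be produced under a rule that classes deeper suppression as failure. The per-visit detected-only figure can be defended as part of a status breakdown. The at-least-once count and the time-to-event cannot.

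A reader might also infer that the measure generally moves against drug effect, so that the ranking of JNJ-56136379+NA against placebo+NA, or of 250 mg against 75 mg, will be reversed. The documents do not support that. Several of the cases above show no reversal. The detection limit is not stated, and protocol inclusion criterion 4 gives untreated subjects an HBV DNA floor (20,000 IU/mL if HBeAg-positive, 2,000 IU/mL if HBeAg-negative) but no ceiling.

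**Conclusion.** The concern holds as a defect of definition. On the SAP's own ordering, the detected-only category is an intermediate, non-nested state. As written, it classes some better outcomes as non-achievement with censoring, and some rebounds as achievement. This needs no assumption beyond the text.

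That a more potent arm can look worse on this row is shown by example. How often it would is not determinable from the documents: it depends on baseline HBV DNA, decline rate and detection limit, all of which were assumed here. Among virologically suppressed subjects, who enter below 60 IU/mL (inclusion criterion 5), any who are not detected at baseline can meet the category only by a rise in HBV DNA. The documents do not say how many there are, so no size is claimed for that group.

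The primary HBsAg analysis, the dose-response analysis and the valid below-LLQ rows are untouched. Severity: minor.

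**What to change.** In Table 5, delete the time to HBV DNA below LLQ with target detected. In Table 4, remove the detected-only category as an achievement, including its at-least-once count by phase and period. Keep the combined and not-detected rows in both tables, and word the combined row so that either result qualifies. Show detected below LLQ only as one of a set of mutually exclusive per-visit statuses: quantifiable, detected below LLQ, not detected, with missing shown separately. One added sentence should state how subjects already below LLQ at baseline are handled in the remaining below-LLQ rows.

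The cost is SAP wording and the matching output specifications: one row out of each table. No data collection changes and no information is lost, because the per-visit statuses carry what the deleted rows held.
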